Cover Page

Outpatient Induction Chemotherapy in Treating
Patients With Acute Myeloid Leukemia or
Advanced Myelodysplastic Syndrome

NCT01807091

Study Protocol with Statistical Analysis Plan

Document date: Feb 20, 2019

**Fred Hutchinson Cancer Research Center
University of Washington
Seattle Cancer Care Alliance**

Current Version: 04/21/2016
Previous Version: 09/03/2015

Title: Feasibility of Outpatient Induction Chemotherapy for Adult Patients with Acute Myeloid Leukemia or Advanced Myelodysplastic Syndrome

Principal Investigator: [name]., PhD
Professor of Medicine
University of Washington
[name]
[name]
[name]
[contact]
[contact]
Email: [contact]

Sub-Investigators:

[name].	Member FHCRC Professor of Medicine UW	[contact]
[name].	Member FHCRC Professor of Medicine UW	[contact]
[name]., PhD	Clinical Associate [name]	[contact]
[name].	Assistant Member FHCRC Assistant Professor of Medicine UW	[contact]
[name]	Member FHCRC [name]	[name]
[name] [name]	Director of Research Development SCCA Research Nurse FHCRC	[contact]
[name], PA-C	Physician Assistant	[contact]
[name]	Project Manager	[contact]

FHCRC IRB Approval

FEB 20 2019

Document Released Date

Seattle Cancer Care Alliance Network Investigators

Sub Investigators

[name]

Evergreen Hospital Medical Center
[contact]

Table of Contents

Section	Page
Table of Contents.....	3
Study Overview.....	4
1. Objectives	4
2. Background and Study Rationale	4
3. Eligibility	5
3.1. Inclusion Criteria	5
4. Treatment Plan.....	6
4.1. Indications for Hospitalization While On Study.....	6
5. Study Procedures.....	7
5.1. Screening Evaluations.....	7
5.2. On Study Evaluations	7
6. Regulatory and Reporting Requirements.....	7
6.1. Adverse Event Monitoring and Reporting.....	7
6.2. Data and Safety Monitoring Plan	8
7. Statistical Considerations	8
8. References.....	10
9. Appendix A.....	11
10. Appendix B - Treatment Related Mortality Score.....	12

Study Overview

This study will be a pilot trial for the feasibility of outpatient induction chemotherapy for diagnosed acute myeloid leukemia (AML) or advanced myelodysplastic syndrome (MDS) for those ages ≥ 18 years of age.

1. Objectives

Assess the feasibility of outpatient induction therapy for acute myeloid leukemia (AML) or advanced (MDS) by examining whether:

- 1.) $>50\%$ of patients treated as outpatients can complete chemotherapy without being admitted to hospital.
- 2.) $<5\%$ of patients die within 14 days of beginning outpatient chemotherapy.

2. Background and Study Rationale

Medical practice over the past 20 years has tried to curb health care costs by increasing outpatient treatment and care for common medical procedures in patients with mainstream conditions. An example of this would be the establishing of "day surgical procedure units". Little focus has been on the "outlier healthcare consumer", those patients that make up a fraction of the population, but disproportionately consume resources¹. Those patients can drive up healthcare cost with a rare, life threatening disease.

Little research has been done to look at the health care economics of acute myeloid leukemia (AML). Commonly today, acute myeloid leukemia (AML) is treated with induction and consolidation chemotherapy in an inpatient hospital setting. Feasibility of outpatient consolidation chemotherapy has been examined², but induction chemotherapy to induce remission in an outpatient setting has not been done.

Research has shown that it is not the LOS (length of stay) fueling the cost of hospital admissions, but front loaded costs; the cost that occur during the "early stage of admission when resource consumption is most intense"³. We have already shown that patients can be safely early discharged once induction therapy is complete. This can be done without an increase in "treatment-related mortality" (TRM) provided the patients are doing well at discharge, live in proximity to UW/SCCA, have an outpatient caregiver, and are committed to return for outpatient follow-up⁴. While we have not quantified the effects of early discharge on cost or quality-of-life, it seems likely that these effects are favorable. We have also shown that, regardless of neutrophil count, patients can be discharged from the hospital after successful treatment of "neutropenic fever" without increase in mortality or admission to the ICU⁵. We have addressed patient safety and early discharge and now want to look one step further. We want to go beyond cost containment of early stage hospital admission and take a look at the feasibility of moving induction chemotherapy for AML patients to an outpatient treatment setting.

This protocol is an extension of our early discharge experience. Specifically it will examine the feasibility of administering to selected outpatients an induction chemotherapy regimen that would usually be administered to inpatients, as will still be the case for most patients. Although administration of the regimen requires only 4-7 days, there could be great cost savings per patient multiplied by many patients and the same seems highly plausible as applied to a patients' quality-of-life.

We will use 2 criteria to assess “feasibility”. The first is whether an excessively high proportion of patients need to be admitted to hospital during administration of chemotherapy because of complications such as vomiting, infection etc. The need to admit a high proportion of patients would at the very least increase work required by providers. Our unpublished experience with outpatient induction is that 15% of a series of 13 patients with relapse were admitted prior to completion of therapy. We propose these data as our historical control, but any specific number will be arbitrary. Certainly the relevance and utility of outpatient therapy would be in doubt were the proportion much above 50%, so we have chosen this number. The 2nd and more important criterion is TRM attributable to administration of typically inpatient chemotherapy to outpatients. “Attributable” is also somewhat nebulous but TRM within 14 days of beginning chemotherapy seems reasonable. Current TRM rates for patients receiving chemotherapy as inpatients are <5%⁶. Hence it would require many patients given chemotherapy as outpatients to be confident that the outpatient TRM rate is similarly low. Such hypothesis testing is not our intent. We merely intend to enter a maximum of 25 patients stopping early should it become likely that our 2 criteria for feasibility will not be met. Our statistical section (see section 7.0) provides the rationale supporting our stopping rules, briefly stated that the study if 7 of 10 patients are hospitalized, or if 3 patients die.

3. Eligibility

Our eligibility requirements have been selected to minimize the chance of TRM and, probably, the need for admission to hospital during the days of chemotherapy administration.

3.1. Inclusion Criteria

- 1.) Signed Written Informed Consent a.)
The signed informed consent.
b.) The benefits / risks of the induction chemotherapy regimen will be reviewed, and a second consent may be necessary if the regimen will be administered according to a separate protocol.
- 2.) AML (APL excepted) or high-risk MDS (10-19% blasts in marrow by morphology or flow cytometry or blood).
- 3.) Meet the eligibility criteria for the selected inpatient protocol that they will receive as an outpatient.

To receive the treatment as an outpatient they must:

- a.) Treatment-related mortality (TRM) score (ref) <9.21 corresponding to a TRM rate of 3% when chemotherapy of similar intensity as proposed here is administered to inpatients.
- b.) Ages ≥ 18 years of age
- c.) Blast count $\leq 10,000$
- d.) Fibrinogen > 200
- e.) Afebrile with clear chest imaging and no signs of active viral, bacterial, fungal infection unless determined to be, at the discretion of the investigator, not clinically significant in the context of this study.
- f.) Adequate cardiac function as demonstrated by LVEF of 45% or greater, by MUGA or echocardiogram. No ongoing cardiac issues such as uncontrolled arrhythmias or unstable angina or congestive heart failure.
- g.) Patient must have an outpatient caregiver available.

- h.) Patient must live within 30 minutes of the treating physician's office during outpatient treatment.
- i.) Patient must be willing to return to the treating physician's office for outpatient follow-up once outpatient treatment is completed.
- j.) Logistical requirements:
 1. Space available in infusion room.
 2. Outpatient infusion pump available if continuous infusion required.
 3. Case discussed with infusion room nursing staff.

Note: age and white blood count are already components of the TRM score, but are included here for safety purposes

4. Treatment Plan

- 1.) Patients will be treated according to the operative inpatient induction chemotherapy regimen for which they will also provide informed consent.
- 2.) Treatment must begin on Monday, Tuesday, Wednesday, Thursday, or Friday after discussion with the 5th floor Infusion Room staff.
- 3.) If treatment includes ara-C at a daily dose of $\geq 1\text{g/m}^2$ patients will receive steroid eye drops and prednisone 100 mg daily or its IV equivalent.
- 4.) Patients must be followed daily during administration of chemotherapy. Evaluation will be until completion of chemotherapy.

Evaluation will include:

- a.) Daily weight
- b.) Daily CBC and platelet count (ordered as "S2D"), chemistries (ordered as S9), and uric acid, LDH, Mg, phosphate
- 5.) Change in weight of +/- 1.5 kg, hematocrit < 24 , platelet count < 10 , sodium < 130 or > 145 , potassium < 3.2 or > 4.8 , fever, or development of fever will mandate a call to the patient's mid level provider or attending physician.
- 6.) Patient will receive prophylactic oral levofloxacin, fluconazole and acyclovir.

4.1. Indications for Hospitalization While On Study

- 1.) Fever (≥ 101.0 F)
- 2.) Infection requiring IV antibiotics.
- 3.) Shortness of breath not promptly responsive to red cell transfusion and/or associated with new infiltrate on chest X-ray.
- 4.) Bleeding not easily halted by platelet transfusion.
- 5.) Any grade 3-4 toxicity (NCI Common Toxicity Criteria) other than myelosuppression, nausea/vomiting controlled by antiemetics, asymptomatic metabolic abnormalities, or skin rash, diarrhea of volume unable to be compensated by oral and IV fluids, pain not controlled by analgesics.

4.2. Mechanism For Care "After Hours" Patients will proceed directly to the local hospital.

5. Study Procedures

All laboratory and radiographic testing mentioned in this protocol will be done as a part of standard of care for patients undergoing induction chemotherapy for AML or advanced MDS.

5.1. Screening Evaluations

- 1.) Complete physical examination.
- 2.) Medical history: Detailed documentation of disease and treatment history with outcomes in standard medical record.
- 3.) ECOG performance status.
- 4.) Concurrent medical conditions.
- 5.) Hematology: CBC with differential and platelet count and peripheral blood smear.
- 6.) Serum chemistries: Electrolytes (sodium, potassium, chloride, and bicarbonate), blood urea nitrogen (BUN), creatinine, glucose, and liver function tests (aspartate aminotransferase (AST) and/or alanine aminotransferase (ALT), alkaline phosphatase (ALP), total bilirubin, DIC panel (includes fibrinogen)
- 7.) Initial standard of care diagnostic bone marrow reports, including hematopathology, cytogenetics/FISH, and flow cytometry.
- 8.) Chest imaging within 7 days of consent.
- 9.) MUGA or echocardiogram within 28 days of consent.
- 10.) Informed consent.

5.2. On Study Evaluations

- 1.) Daily weights during induction chemotherapy administration.
- 2.) Provider (physician or advanced practice provider) visit including elicitation and documentation of adverse events as well as symptom-focused physical exam on days 1, 3, and 5 of induction chemotherapy.
- 3.) Hematology: CBC with differential and platelet count daily during induction chemotherapy then as standard of care; DIC panel days 1 and 2 of induction chemotherapy and then as needed.
- 4.) Serum chemistries: Electrolytes (sodium, potassium, chloride, and bicarbonate), BUN, creatinine, glucose, and liver function tests (AST, ALT, ALP, total bilirubin, LDH) and tumor lysis labs (Ca, Mag, phos, uric acid, LDH) daily during induction chemotherapy.
- 5.) Hospitalization and reason for hospitalization during induction will be monitored.
- 6.) Mortality during the first 14 days will be monitored.

6. Regulatory and Reporting Requirements

6.1. Adverse Event Monitoring and Reporting

The principal investigator is responsible for monitoring the safety of patients who enroll in the study. This protocol will not dictate the choice of chemotherapy regimens. The sole research focus of this study is the feasibility of using an outpatient setting for administration of chemotherapy for AML or advanced MDS. For purposes of this study, only the following AEs will be recorded:

- 1.) Reasons for hospitalization during planned outpatient administration of chemotherapy.
- 2.) Causes of any deaths that occur within 14 days of start of outpatient chemotherapy (expedited reports).

6.2. Data and Safety Monitoring Plan

Ongoing trial oversight is carried out by the principal investigator, [name] and the primary research nurse. These individuals will meet regularly to review recently acquired data, and adverse events. Institutional support of trial monitoring is provided in accordance with the FHCRC Institutional Data and Safety Monitoring Plan. Under the provisions of this plan, the FHCRC research Trials Office coordinates monitoring of data accuracy and compliance by consultants, contract research organizations, or FHCRC employees unaffiliated with the conduct of the study. Independent monitoring visits occur at specified intervals determined by the assessed risk level of the study and the findings of previous visits. In addition, protocols are reviewed at least annually by the Protocol and Data Monitoring Committee (PDMC) and the Institutional Review Board (IRB). The PDMC reviews accrual, adverse events, stopping criteria, and adherence to the data and safety monitoring plan. The PHCRC IRB reviews the study progress and safety information to assess continued acceptability of the risk-benefit ratio for human subjects. Approval of both committees is necessary to continue the study.

7. Statistical Considerations

A maximum of 25 patients will be entered. Stopping earlier would happen under 2 circumstances:

- 1.) Excess probability that patients have to be admitted to hospital during the 4-7 days of outpatient chemotherapy.
- 2.) Excess probability that patients die during the 14 days after beginning outpatient treatment.

For both 1 and 2 the case for stopping will be evaluated using the program "predictive probabilities" freely available from the Statistics Department at MD Anderson Cancer Center (<https://biostatistics.mdanderson.org/softwaredownload/>). In particular stopping will occur based on the Bayesian inequality probability $\Pr[\pi_i > \pi_j] > 0.90$ where \Pr = probability, π_i is the posterior probability for rate of admission to the hospital with current management and π_j the probability of rate of admission with former management. We will assume that π is distributed $\beta(a,b)$ where "a" is the number of successes (no admission) and "b" the number of failures (admission) with management approach i (current) or management approach j (previous). We will assume a prior of $\beta[25,25]$ for the previous approach corresponding to a 50% need for hospital admission with prior outpatient management in 50 patients and a prior of $\beta(5,1)$ with the current approach corresponding to our data indicating that 5 patients have been treated as outpatients without need for inpatient admission while 1 has been admitted. As patients up to a maximum of 25 are entered on the current approach its prior will be updated and compared to the $\beta[25,25]$ distribution using the inequality probability 0.90 noted above. With this configuration here are the predictive probabilities that the current approach (called A) is truly better than the previous approach $\beta[25,25]$ denoted B given various numbers of successes (no admission during days 4-7) and failures (admission).

Successes (No admission)	Failures (Admission)	Predictive Probability A (current) better than B (Previous)
1	0	0.95
0	1	0.74
0	2	0.51
0	3	0.31
0	4	0.16
0	5	0.07
1	6	0.05
1	5	0.12
2	6	0.09
3	6	0.15
3	7	0.06

We would stop accrual should the predictive probability be < 0.10 , for example in the 3 success / 7 failure scenario noted above. In this case 7 patients of 10 patients would have been admitted contrasted with the maximum acceptable rate of 4 admitted / 6 not.

For the death within 14 days endpoint our prior for the current (inpatient) approach will be $\beta[49, 1]$ corresponding to a 2% (1/50) death rate and will be $\beta[5, 0]$ for the outpatient approach, corresponding to 0 deaths in the 5 patients who would have met eligibility criteria for the proposed protocol. These data will be updated as patients (up to the maximum of 25) are enrolled and the resultant beta distribution compared to the $\beta[49, 1]$ distribution noted above, using the inequality probability 0.9 noted in the section on admission to the hospital. With this configuration here are the predictive probabilities that the current approach (called A) is truly worse than the previous approach $\beta[49, 1]$ denoted B given various numbers of successes (no deaths days 1- 14) and failures (deaths days 1- 14).

Success (No death within 14 days)	Failure (death within 14 days)	Predictive Probability A (current) worse than B (Previous)
1	0	0.05
0	1	0.28
0	2	0.97
1	2	0.95
4	2	0.90
5	2	0.88
21	3	0.99

We would stop accrual should the predictive probability be > 0.90 , for example in cases where there are 2 failures and < 5 successes, or in any case where there are 3 deaths.

8. References

1. Moroney SD. Understanding Health Care Cost Drivers. National Institute of Health Policy. 2003.

9. Appendix A

PERFORMANCE STATUS CRITERIA

ECOG Performance Status Scale		Karnofsky Performance Scale	
Grade	Descriptions	Percent	Description
0	Normal activity. Fully active, able to carry on all pre-disease performance without restriction.	100	Normal, no complaints, no evidence of disease.
		90	Able to carry on normal activity; minor signs or symptoms of disease.
1	Symptoms, but ambulatory. Restricted in physically strenuous activity, but ambulatory and able to carry out work of a light or sedentary nature (e.g., light housework, office work).	80	Normal activity with effort; some signs or symptoms of disease.
		70	Cares for self, unable to carry on normal activity or to do active work.
2	In bed <50% of the time. Ambulatory and capable of all self-care, but unable to carry out any work activities. Up and about more than 50% of waking hours.	60	Requires occasional assistance, but is able to care for most of his/her needs.
		50	Requires considerable assistance and frequent medical care.
3	In bed >50% of the time. Capable of only limited self-care, confined to bed or chair more than 50% of waking hours.	40	Disabled, requires special care and assistance.
		30	Severely disabled, hospitalization indicated. Death not imminent.
4	100% bedridden. Completely disabled. Cannot carry on any self-care. Totally confined to bed or chair.	20	Very sick, hospitalization indicated. Death not imminent.
		10	Moribund, fatal processes progressing rapidly.
5	Dead.	0	Dead.

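### The sentence that defines the admission stop contradicts its own beta definition and the table rule, and on neither reading does it stop at the plan's own example of 7 admitted in 10

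*Combined protocol and SAP*

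**What the plan says.** Section 7 gives two stopping circumstances. The first is "Excess probability that patients have to be admitted to hospital during the 4-7 days of outpatient chemotherapy". For this one the text contains three statements that should describe one rule:

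- **The defining sentence.** "In particular stopping will occur based on the Bayesian inequality probability" Pr[π_i > π_j] > 0.90, where π_i "is the posterior probability for rate of admission to the hospital with current management" and π_j is the same for former management.
- **The distribution of π.** π is beta(a, b), where a "is the number of successes (no admission") and b is the number admitted. The previous approach is beta(25, 25) and the current approach starts at beta(5, 1), that is, 5 not admitted and 1 admitted. The current distribution is updated for up to 25 patients and compared "using the inequality probability 0.90 noted above".
- **The table and cutoff.** "here are the predictive probabilities that the current approach (called A) is truly better than the previous approach", for 11 outcomes, none beyond 10 patients. Accrual stops when this value is below 0.10, "for example in the 3 success / 7 failure scenario noted above" (printed value 0.06), "contrasted with the maximum acceptable rate of 4 admitted / 6 not".

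Section 2 also gives 7 hospitalized of 10 as the stopping rule.

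**The concern.** The defining sentence treats π as a bad outcome, while the beta parameters and both priors make it a good one. Under the second meaning, exceeding 0.90 is evidence in favour of outpatient treatment, so the sentence would stop the trial for success. Under the first meaning the direction is right, but the quantity is the current posterior probability, whereas the table is headed as a predictive probability and acted on at 0.10.

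Stopping for admissions is one of only two decision rules in the trial. The table covers few of the outcomes that can occur in 25 patients. For any other outcome, the study team and the monitoring committee must compute from the text, and the text defines a different quantity from the one in the table.

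**Working it through.** **Inputs (all Section 7).** Previous approach B: Y ~ beta(25, 25), fixed. Current approach A after s not admitted and f admitted: X ~ beta(5+s, 1+f). Maximum 25 patients. Cutoffs 0.90 and 0.10.

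**1. Reproduce the table.** The posterior probability that A is better is

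Pr(X > Y) = ∫ f_X(x) F_Y(x) dx.

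At 25 patients this is 0.904 with 15 not admitted and 0.844 with 14, so exceeding 0.90 needs at least 15 of 25 not admitted. The predictive probability of getting there is the beta-binomial sum

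PP(s, f) = Σ BetaBin(k; 25−s−f, 5+s, 1+f), over k ≥ 15−s.

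For 3 not admitted and 7 admitted, at least 12 of the remaining 15 must avoid admission under beta(8, 8): 0.0390 + 0.0180 + 0.0060 + 0.0011 = 0.0641.

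| Not admitted / admitted | Printed | PP | Pr(X > Y) now |
|---|---|---|---|
| 1 / 0 | 0.95 | 0.954 | 0.98 |
| 0 / 1 | 0.74 | 0.739 | 0.88 |
| 0 / 2 | 0.51 | 0.515 | 0.76 |
| 0 / 3 | 0.31 | 0.310 | 0.63 |
| 0 / 4 | 0.16 | 0.161 | 0.50 |
| 0 / 5 | 0.07 | 0.071 | 0.39 |
| 1 / 6 | 0.05 | 0.052 | 0.40 |
| 1 / 5 | 0.12 | 0.125 | 0.50 |
| 2 / 6 | 0.09 | 0.093 | 0.50 |
| 3 / 6 | 0.15 | 0.150 | 0.59 |
| 3 / 7 | 0.06 | 0.064 | 0.50 |

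All 11 printed values match PP to within 0.005. None is the probability that A is truly better, which is the last column.

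**2. Defining sentence, π read by its beta parameters (no admission).** Stop if Pr(X > Y) > 0.90. Before any patient enrols this is 0.962, so the condition is already met, and it rises with good results (0.980 after one patient not admitted). With 4 admitted and 6 not, the result the plan calls the maximum acceptable rate, it is 0.915, again a stop; with 5 and 5 it is 0.817. At 7 admitted in 10, X ~ beta(8, 8). Both distributions are symmetric about 0.5, so the value is exactly 0.50 and there is no stop.

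**3. Defining sentence, π read as the admission rate.** Stop if 1 − Pr(X > Y) > 0.90. At the prior this is 1 − 0.962 = 0.038. With 9 of 9 admitted it is 0.882, and with 10 of 10 it is 0.915, so 10 of 10 is the earliest possible stop (9 of 10 gives 0.817). At 24 patients 19 admissions are needed. At 7 of 10 the value is again 0.50, with no stop.

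**4. Boundary of the table rule (PP < 0.10).** Fewest admissions that stop accrual:

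| Patients | 5 | 6–8 | 9–10 | 11–13 | 14–16 | 17–20 | 21–24 |
|---|---|---|---|---|---|---|---|
| Admissions | 5 | 6 | 7 | 8 | 9 | 10 | 11 |

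**5. Consequence.** Exact recursion, with a look after every patient through 24:

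| True admission rate | Table rule: stops | Table rule: mean enrolled | Admission-rate inequality: stops | Admission-rate inequality: mean enrolled |
|---|---|---|---|---|
| 70% | 99.7% | 9.8 | 32% | 22.6 |
| 60% | 95% | 13.2 | 8% | 24.4 |
| 50% | 75% | 17.7 | 1.0% | 24.9 |

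If the result at 25 is also counted, the stop probabilities are 99.8%, 97% and 80% against 38%, 10% and 1.3%.

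**The case against.** The best defence is that the operative rule can be recovered. Section 7 names a predictive-probability program, prints predictive probabilities, states the 0.10 cutoff and works an example that Section 2 repeats. If 0.90 is taken as the criterion applied at 25 patients inside that calculation, with π as no admission, everything fits. Even the remark about 4 admitted and 6 not fits, since 4 of 10 is the most admissions in 10 that still meets 0.90 and is the same 40% as 10 of 25. On the admission-rate reading, the direction and threshold also agree with the table rule, because a probability above 0.90 that admissions are higher is a probability below 0.10 that A is better; only posterior versus predictive differs. Nobody holding the table would stop a trial at its prior.

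Much of this stands, and it shows which rule was probably meant. It does not rescue the sentence. The coherent reading has to discard both the description of π as an admission rate and the statement that stopping occurs when the probability exceeds 0.90. The table cannot settle the matter alone: it ends at 10 patients, and any cutoff from about 0.844 to just under 0.904 gives the same 15-of-25 requirement and hence the same values.

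It is also fair that the stop probabilities in the working compare the intended rule with a misreading rather than showing a loss that has occurred, and that the plan fixes no schedule of looks. The 50% row is the comparator rate; Section 2's doubt concerns rates well above it.

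**Conclusion.** The point holds and needs correcting. The sentence that formally defines the admission stop is wrong as written: its two definitions of π are incompatible, and under either one it gives 0.50, and no stop, at the 7 of 10 for which Sections 2 and 7 both call for stopping. The table, the 0.10 cutoff and the worked example are sound and agree with each other. The 0.90 acts as the success criterion at 25 patients, which the text never states.

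Applied literally as an admission-rate comparison, the sentence would cut the chance of stopping at a true 70% admission rate from 99.7% to 32%, and raise mean enrolment from 9.8 to 22.6 patients. Those figures assume the printed priors, independent patients with a constant admission rate, and a look after each patient through 24. The contradiction itself rests on no assumption about looks.

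**What to change.** The sponsor should confirm that the table rule is the intended one. If so, in Section 7:

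1. Define π as the probability of completing chemotherapy with no admission.
2. Replace the inequality sentence with: *Accrual stops if the predictive probability that Pr(π_A > π_B) > 0.90 at 25 patients is below 0.10.*
3. Relabel the table column as the predictive probability of concluding that A is better at 25 patients, and drop the claim that it is the probability of A being truly better.
4. Print the boundary from step 4 of the working, state that the criterion at 25 patients is met with 10 or fewer admissions, and refer to the boundary from Section 2, whose 7 of 10 is one point on it.
5. State the operating characteristics. The rule stops about 9% of the time at a true 30% admission rate and 38% at 40% (11% and 43% counting the result at 25). State also that it requires 15 of 25 not admitted, whereas Objective 1 (more than 50%) requires 13.

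Items 1 to 3 remove the contradiction; items 4 and 5 make the rule usable beyond the printed rows. Two smaller matters can be settled in the same edit. The text above the table refers to admission on days 4 to 7, where the start of Section 7 means a course lasting 4 to 7 days. The death rule borrows the same 0.90 inequality, so its wording should be checked against the revised sentence.

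The cost is protocol wording only. Priors, thresholds, table values, the worked example and the sample size do not change.

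### Does it matter that Objective 1 speaks of completing chemotherapy, while Section 7 scores only hospital admission?

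*Combined protocol and SAP*

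**What the plan says.** Section 1, Objective 1, sets the target that more than 50% "of patients treated as outpatients can complete chemotherapy without being admitted to hospital". Read word by word, this has two elements: the patient finishes the course, and is not admitted.

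The rest of the plan carries only the second element:

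- Section 2 names two feasibility criteria and describes the first as "whether an excessively high proportion of patients need to be admitted to hospital during administration of chemotherapy".
- Section 5.2 lists two outcome items: "Hospitalization and reason for hospitalization during induction will be monitored" and "Mortality during the first 14 days will be monitored".
- Section 6.1 states "For purposes of this study, only the following AEs will be recorded", then gives reasons for hospitalization and causes of death within 14 days.
- Section 7 gives the first reason for early stopping as "Excess probability that patients have to be admitted to hospital during the 4-7 days of outpatient chemotherapy". It then defines the beta parameters by admission or no admission, and introduces the table with "given various numbers of successes (no admission during days 4-7) and failures (admission").

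Section 4 requires daily follow-up while chemotherapy is given, with evaluation continuing until it is complete.

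**The concern.** A patient could stop before the last planned dose, or die at home, without being admitted. Section 7 would score that patient as a success, although Objective 1 taken literally would not. Two analysts could then report different Objective 1 results from the same 25 patients.

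The stopping rule appears to sharpen the point. It removes trials with many admissions, so a trial that reaches 25 patients will nearly always have more than half unadmitted. If Objective 1 means admission only, it looks as if it is met by construction at full accrual. Completion would then be the only element left that could fail, and it is the one the plan does not record.

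The table's introductory sentence adds a smaller worry. Taken literally, no admission during days 4-7 would ignore admissions on days 1 to 3.

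**Working it through.** **Inputs (Section 7).** Current approach A has prior beta(5,1). Previous approach B is beta(25,25). The maximum is 25 patients, the inequality threshold is 0.90, and accrual stops when the predictive probability falls below 0.10. Section 2 gives a historical admission rate of 15% in 13 patients. No document gives a rate of stopping early without admission, so every such rate below is an assumption.

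**Reproducing the plan's table.** With f admissions among 25 patients, A's final distribution is beta(30 − f, 1 + f).

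- f = 10 gives Pr(A > B) = 0.904.
- f = 11 gives Pr(A > B) = 0.844.

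The 0.90 threshold therefore requires at most 10 admissions, that is, at least 15/25 unadmitted. The tabulated figure is the beta-binomial probability of ending with at most 10 admissions, given the data so far. All 11 rows reproduce within 0.005: 0.954, 0.739, 0.515, 0.310, 0.161, 0.071, 0.052, 0.125, 0.093, 0.150 and 0.064, in the plan's order.

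**Stopping boundary.** With a check after each patient, accrual stops at 5 admissions for n = 5, 6 for n = 6–8, 7 for n = 9–10, 8 for n = 11–13, 9 for n = 14–16, 10 for n = 17–20 and 11 for n = 21–24. A trial still open after patient 24 has at most 10 admissions. It therefore has at most 11 at patient 25, which leaves 25 − 11 = 14 unadmitted (56%).

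**How many non-completers change the answer.** More than 50% of 25 means at least 13. With 11 admitted, 2 unadmitted non-completers leave 12/25 (48%). With 10 admitted it takes 3. With 4 admitted, close to the historical 15% (0.15 × 25 = 3.75), it takes 9.

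**How often that would happen.** Let a be the admission rate and c the proportion of all patients who stop early unadmitted. Among unadmitted patients the non-completion rate is then c/(1 − a). Among trials reaching 25, the chance of at most 12 unadmitted completers is

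Σ over f ≤ 11 of P(f admitted, not stopped) × P(Bin(25 − f, 1 − c/(1 − a)) ≤ 12), divided by P(reach 25).

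One term as an example, with a = 40% and c = 5%: c/(1 − a) = 0.05/0.60 = 0.083. At f = 11 the chance of 2 or more non-completers among 14 is 1 − 0.9167^14 − 14 × 0.0833 × 0.9167^13 = 0.328. The share of trials reaching 25 with f = 11 is 0.0884, so this term adds 0.0884 × 0.328 = 0.029. The other terms bring the total to 0.070.

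| Admission rate a | c = 2% | c = 5% | c = 10% |
|---|---|---|---|
| 15% (Section 2) | below 0.1% | below 0.1% | 0.3% |
| 35% (assumed) | 0.5% | 3.9% | 17.6% |
| 40% (assumed) | 1.0% | 7.0% | 27.4% |

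If 5% or 10% is instead taken among unadmitted patients, the 40% row becomes 2.4% and 10.1%.

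**Is completion the only element that can still fail?** Not in general, for two reasons.

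- The minimum of 14/25 depends on a check after every patient with no outcomes pending, and Section 7 states no interval. With checks every 5 or 10 patients, 14 admissions are possible, and at a true 40% rate about 2% of trials reaching 25 have 12/25 or fewer unadmitted.
- On the plan's own 0.90 inequality, 14/25 fails (0.844). At 40% admission, 8.8% of trials reaching 25 end there. The admission element can thus still miss the plan's own standard at full accrual.

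**The days 4-7 wording.** The opening of Section 7 describes the window as the 4-7 days of chemotherapy, which is a duration. The beta definition and the table headings carry no day limit. Reading the phrase as that duration changes no table value and no boundary.

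**The case for a change.** The best argument for a change is that Objective 1 is one of only two objectives, its wording includes completion, and the remedy is cheap: one yes/no item with a reason, and two sentences on scoring. It is true that no section lists completion as an outcome or says how to score an unadmitted patient who stops early. The daily evaluation in Section 4 sets the length of follow-up and does not make completion an endpoint. This much stands.

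It does not carry the case for a change, for four reasons.

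- Sections 2, 5.2 and 7 agree on admission as the criterion. One phrase in Section 1 differs, and it reads naturally as getting through the course unadmitted.
- The affected group is probably small. The course lasts 4 to 7 days, and Section 4.1 makes fever, infection needing IV antibiotics, bleeding not easily controlled and most grade 3-4 toxicity indications for hospitalization. Most toxicity that would end a course early should therefore already count as an admission. Deaths within 14 days are captured under Objective 2.
- The information should not be lost. Patients are seen daily, the treatment record shows what was given, and the restriction in Section 6.1 concerns adverse events, which completion is not.
- Counting every early stop as a failure of outpatient feasibility is itself debatable, since some stops have nothing to do with the setting. A composite would also leave the stopping rule monitoring something other than the objective.

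**Conclusion.** No change follows. The plan has a small gap in detail that an analyst can fill sensibly: report the proportion not admitted, report beside it the proportion who received all planned chemotherapy without admission, and list any early stops by reason. Neither needs a change to the sample size, priors, table or stopping boundary. Rewording Objective 1 as admission only would serve equally well. The days 4-7 wording is a clerical slip that Section 7 itself resolves.

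The effect is about 0.3% or less of trials reaching 25 patients at the protocol's 15% admission rate, for non-completion up to 10% of all patients. It becomes appreciable, at 3.9% to 27.4%, only if 35% to 40% are admitted and 5% to 10% stop early unadmitted. Those admission rates are more than twice the historical figure, and the non-completion rates have no source in the documents. The calculation assumes a check after each patient, independent outcomes, and more than 50% read as an observed proportion. If non-completion without admission does not occur, the two readings of Objective 1 coincide. For a pilot of at most 25 patients that disclaims hypothesis testing, this is an optional point of wording.
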